**Strategy to address heterogeneity of treatment effect:** Subgroup analysis is the most commonly used analytic approach for examining HTE, and we will utilize an exploratory variant of this analysis in our approach. Definition of subgroups, endpoints, hypotheses, and modeling parameters will be derived in response to the data. An example of this would be the use of a backward model selection approach to identify treatment by covariate interactions. Some of the important types of subgroup variables will be: (1) demographic variables (e.g., age); (2) pathophysiologic variables (e.g., timing after recurrence, disease grade); (3) comorbidities (e.g., presence of diabetes); and (4) concomitant exposures (e.g., hormone replacement therapy, proton pump inhibitors). Additionally, “non-traditional” characteristics that affect patient decision-making (e.g. social support, patient decision-making style, disease related anxiety, baseline quality of life) will be collected to improve risk-adjustment and increase the individualization of the results. Although it is extremely difficult to obtain the sampling properties of subgroup effect estimators (e.g., standard errors), post hoc exploratory subgroup analyses may identify promising hypotheses that will be subject to more rigorous future examination.

**Strategy to address confounding by selection bias:** Observational studies (like our proposed investigation) that lack randomization of subjects into treatment groups and must address selection bias to properly estimate the effect of treatment. We will apply a propensity scoring method (PSM) and instrumental variable (IV) method to adjust for observed and unobserved confounding, respectively. Propensity scoring will be used to mitigate the expected biases from observed confounding in the proposed observational study. It is a balancing score that effectively makes the distribution of measured baseline covariates similar between treatment groups. This is important because the apparent difference in outcome between those treated with endoscopic dilation versus those treated with endoscopic resection or open anterior neck surgery may depend on characteristics that affected whether or not a patient received a given treatment instead of due to the actual effect of the treatment. This issue is relevant to our study Aims #2 and #3, but for illustrative purposes, the specific analytic approach will be described in the context of Aim #2. Its objective is to determine factors that affect time to stenosis recurrence in patients with idiopathic subglottic stenosis. In this analysis, the dependent variable is time to recurrence and the primary independent variable is treatment type: endoscopic dilation versus endoscopic excision or open anterior neck surgery of the affected portion of the trachea.

There are three basic techniques for propensity score method: matching, stratification, and regression. We plan to use two-step process of stratification and regression. Stratification consists of grouping subjects into strata determined by observed background characteristics; then comparing subjects between treatment groups directly. Propensity scoring on strata is particularly useful when there are large numbers of covariates, as is the case in this study. Conventionally, creation of five strata has been shown to remove 90% of bias due to the stratified variable. The propensity score is then estimated using a logistic regression model, in which the treatment status is regressed on observed and stratified baseline characteristics. This allows for the formation of matched sets of patients who underwent endoscopic dilation, endoscopic resection or open anterior neck surgery for their iSGS based on similar propensity score values. In essence, all collected and known confounding covariates will be collectively replaced by a single function of these covariates – the propensity score. Thus, the collection of known predictors is collapsed into a single predictor. Since time to recurrence is a continuous variable, the effect of treatment will be estimated as the difference between the mean time for patients in the endoscopic dilation versus endoscopic resection or open anterior neck surgery groups. Once treatment effect has been estimated using propensity scoring, variance of outcome effect and statistical significance can be estimated. Analysis of the propensity matched treatment groups can be accomplished by directly comparing outcomes between the three treatment groups. Multivariate regression will be performed to reduce bias due to residual differences in observed baseline covariates between groups.

All known and measurable covariates and confounders will be collected and considered in the propensity score model. Incorporation to the multivariate model will be determined *a priori* based on their potential to confound or modify the association between treatment and time to recurrence, and include **demographics** (age, sex, race, socioeconomic status, geographic location, marital status), **health** (Charlson-Deyo score, body mass index), **endocrinologic history** (age of first menses, number of pregnancies, onset of menopause, use of hormone replacement therapy), **Inflammatory biomarkers** (high sensitivity CRP, Antinuclear Antibodies, Antineutrophil

Antibodies, Renal filtration rate), **anatomic** characteristics (airway scar length, degree of luminal obstruction, distance from the glottis), **physiologic** (gastroesophageal reflux disease testing, pulmonary function testing), **social/behavioral** [Social Support (FSSQ), Quality of life (SF12), Decision-making style (PDMstyle), Fear of Progression (FoP-Q-SF)]. Provider-specific covariates will include the type of subspecialty training program, training location, procedural volume, and treatment criteria for open anterior neck surgery. In addition, the model will include interaction terms for the associations of age with endocrinologic history, Charlson-Deyo score, and facility regions based on statistical evidence of effect modification and theoretical plausibility.

Propensity scoring can only adjust for observed confounding variables such as those listed above not unobserved ones. Therefore, we will employ quantitative and limited variable (QLIM) to conduct instrumental variable analysis to adjust for unobserved confounding. The instrumental variable has to meet five specific assumptions: 1) potential outcomes for each patient are unrelated to treatment status of other patients, 2) instrument affects receipt of the treatment of interest, 3) this effect is always in the same direction, 4) instrument assigns treatment randomly, and 5) instrument has an effect on the outcome only through the treatment assignment. The instrument that we plan to use in this analysis is distance from the patient's residence to the treating facility. The assumption is that the association between distance to the hospital and time to recurrence is due only to the effect of relative distance on treatment assignment after controlling for observed variables and not directly correlated with time to recurrence. This process will involve a two-stage process that first uses the instrument variable and other covariates to predict the treatment. A second stage estimates the outcome by the predicted treatment (from the first model) and other covariates. Using a two-stage approach has the advantage of incorporating the predicted treatment into the outcome model as it represents the portion of treatment selection related to distance from the treating facility. We will also adjust, when possible, for any instrument-outcome confounding, as confounding can still occur even with the instrumental variable procedure. Other instruments will be considered if distance to treating facility is not found to meet the aforementioned assumptions or is found to significantly confound the outcome.

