## **STATEMENT OF COMPLIANCE**

The study will be conducted in accordance with the International Conference on Harmonisation guidelines for Good Clinical Practice (ICH E6), the Code of Federal Regulations on the Protection of Human Subjects (45 CFR Part 46), and the PCORI Clinical Terms of Award. All personnel involved in the conduct of this study have completed human subjects protection training.

[figure not shown]
Title:	Treatment Alternatives in Adult Rare Disease; Assessment of Options in Idiopathic Subglottic Stenosis
Précis:	The proposed study intends to create an international, multi-institutional prospective cohort of iSGS patients. It will enable rigorous treatment strategy comparisons to determine how well the most commonly used treatments in iSGS “work”; and what quality of life trade-offs are associated with each approach.
Objectives:	
Prospective rigorous treatment comparisons to provide the critical information to patients to allow them to answer the questions,
 

1) “given my personal characteristics, conditions and preferences, what should I expect will happen to me?” and

2) “what are my options and what are the potential benefits and harms of these options?”

 
Primary Endpoint: Treatment effectiveness: time to recurrent procedure and need for tracheostomy.
 
Secondary Endpoint: Health and quality of life tradeoffs: patient reported outcome measures in voice, swallowing, breathing, and global quality of life

Population:	All clinically confirmed iSGS patients at the participating institutions are eligible for enrolment.
Number of Sites:	45 Sites
Study Duration:	60 months
Subject Participation Duration:	>6months
Estimated Time to Complete Enrollment:	24 months

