In contrast to the retrospective nature of RP-01, our proposed PR-02 prospective study design will directly compare effectiveness of contemporary treatments and assess their associated quality of life tradeoffs in iSGS patients. While evaluating treatment effectiveness is important, it is equally critical that the patient experience with the disease itself and its treatment be systematically characterized. This is imperative since patient and physician perspectives are often significantly discordant. To this end, NoAAC PR-02 will collect patient-reported outcomes (PROs) in the cohort at initial presentation and at *a priori* determined intervals thereafter, (e.g. immediately pre-intervention, as well as 3, 6, and 12 months post-intervention) and conduct patient interviews and focus groups (labeled “engagement studios”) to better understand the patient experience with this condition.

Beyond the gaps in understanding of the relative effectiveness of clinical outcomes, no studies have explored health-related quality of life (HRQOL) or functional outcomes in iSGS. These endpoints are important to patients and are arguably a primary determinant in decision-making. For example, results show that endoscopic dilation is associated with a higher rate of disease recurrence and thus need for repeated surgery. Meanwhile, open cricotracheal resection is a major surgery with significant immediate perioperative risks and has been associated with alterations in voice and swallowing. Open surgery appears to reduce the risk of disease recurrence, but the degree of benefit, and the trade-offs associated with this invasive surgery are questions that demand prospective study.

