#### **11.0 Study Withdrawal/Discontinuation**

Study participants may withdraw from the study at any time by contacting the site specific PI, or the Coordinating Center PI [name], or coordinating center research team staff.

Subjects are free to withdraw from participation in the study at any time upon request.

An investigator may terminate a study subject's participation in the study if:

- Any medical condition, event or situation occurs such that continued participation in the study would not be in the best interest of the subject.
- The subject meets an exclusion criterion (either newly developed or not previously recognized) that precludes further study participation.

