### **Final Analysis Plan**

**The primary objective:** The primary objective of this study is to evaluate the time to recurrence (TTR) among three possible treatment groups, i.e., open surgery, endoscopic dilation, and endoscopic resection.

**Data analysis plan for the primary endpoint:** Demographic information will be tabulated. Descriptive statistics, including means, standard deviations, and ranges for continuous parameters, as well as percents and frequencies for categorical parameters, will be presented. For the primary objective analysis, i.e., estimating the TTR with 95% confidence interval, the TTR time will be estimated using the Kaplan-Meier method with the 95% confidence interval (CI). The Rothman CI, CI's based on Greenwoods variance, Thomas and Grunkemeier CI and the simultaneous confidence bands by Nair and Hall and Wellner will be reported. The logrank test will be used to compare the equality of survival curves. The generalized Wilcoxon and log-likelihood tests will also be examined, as these tests weight the survival function differently from the logrank test, which gives more weight to later occurring events. The Cox proportional hazards model will be applied to investigate potential prognostic factors, such as age on the TTR data. The adjusted p-values as well as the adjusted 95% confidence intervals from the Cox model will be reported. The adjusted hazard ratios and 95% CIs will be reported.

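### The propensity-score analysis compares mean times to recurrence with no rule for patients who have not recurred and no time horizon

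*Combined protocol and SAP*

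**What the plan says.** Section 12.0 makes time to recurrence (TTR) the primary endpoint. The primary-endpoint plan uses Kaplan-Meier curves, logrank and related tests, and a Cox model for prognostic factors such as age. Of the Cox model it says: "The adjusted hazard ratios and 95% CIs will be reported".

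Treatment is not randomised, so the section adds a strategy against selection bias. Observed confounding is given to the propensity score: "Propensity scoring will be used to mitigate the expected biases from observed confounding in the proposed observational study". The effect measure for that analysis is then stated together with its reason: "Since time to recurrence is a continuous variable, the effect of treatment will be estimated as the difference between the mean time for patients" under dilation and under resection or open surgery. A regression for residual covariate imbalance follows, with no model named. For unobserved confounding, an instrumental-variable analysis is planned: "A second stage estimates the outcome by the predicted treatment (from the first model) and other covariates".

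Three other places bear on whether TTR is fully observed:

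- In the protocol summary, the row "Subject Participation Duration" gives more than 6 months, within a 60-month study with 24 months of enrolment.
- Section 11.0 says: "Subjects are free to withdraw from participation in the study at any time upon request".
- Section 1.0 says: "Open surgery appears to reduce the risk of disease recurrence".

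The missing-data strategy covers patient-reported outcomes only. No censoring rule for TTR appears in the text.

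**The concern.** A simple mean needs a recurrence time for every patient. Patients who have not recurred at last contact have none, and there should be more of them after open surgery if it does reduce recurrence. The analyst must then drop them, count their follow-up as if it ended in recurrence, or take the mean from a survival curve up to some horizon. The plan chooses none of these. Its stated reason, that the variable is continuous, points to an ordinary mean.

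This is the analysis that the plan relies on for observed confounding in a non-randomised comparison. Two analysts could follow the text and report very different effects. Either result could disagree with the Cox hazard ratios for reasons unrelated to confounding, and a reader might wrongly take the disagreement as evidence of confounding.

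**Working it through.** **Plan's own figure.** None exists for this estimator. The only design figures are half-widths for the recurrence function (below .24 and .13), and they do not bear on a difference in means.

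**Inputs.**

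- From the protocol summary: 24 months of enrolment and a 60-month study. If everyone is followed to study end and entry is uniform, follow-up C is uniform on 36 to 60 months.
- From Section 1.0: a median of 1.75 surgeries per year (95% CI 0.8 to 2.6), pooled over treatments. I borrow 0.8 as an assumed dilation rate.
- Assumed, with no source in the documents: open-surgery rates of 0.05 to 0.2 per year, exponential recurrence times and non-informative censoring.

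**Formulas.** The monthly rate is λ and C is uniform on (a, b).

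- Proportion recurring: P = 1 − (e^(−λa) − e^(−λb)) / (λ(b − a))
- Mean over recurrent patients only: 1/λ − E[C·e^(−λC)] / P
- Mean with censored times counted as recurrences: P/λ
- Restricted mean to horizon τ: (1 − e^(−λτ)) / λ

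**Case 1: equal follow-up of 36 to 60 months, 0.8 v 0.1 per year** (1/λ = 15 and 120 months).

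- Dilation: P = 1 − (0.0907 − 0.0183)/1.6 = 0.955, so 4.5% are censored. Open: P = 1 − (0.7408 − 0.6065)/0.2 = 0.329, so 67% are censored.
- Recurrent patients only: dilation 15 − 2.03/0.955 = 12.9; open 120 − 31.96/0.3286 = 22.7. Difference **9.9 months**.
- Censored as recurrences: dilation 0.955 × 15 = 14.3; open 0.3286 × 120 = 39.4. Difference **25.1 months**.
- Restricted mean difference: 9.8 at 24 months, 17.5 at 36 and 25.2 at 48.
- Unrestricted means differ by 120 − 15 = 105 months. This is far beyond the 60-month study, so it could not be estimated without extrapolation.

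The two literal readings differ by a factor of 25.1/9.9 = 2.5. Over dilation rates of 0.8 to 2.6 and open rates of 0.05 to 0.2 per year, the factor runs from 28.25/16.40 = 1.7 to 29.10/10.74 = 2.7.

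**Case 2: 85% of open patients never recur and the rest recur at 0.8 per year.** Recurrent patients then have the same mean in both groups, so the recurrent-only difference is 0.0. The 36-month restricted mean for open surgery is 0.15 × 13.64 + 0.85 × 36 = 32.65, so the true difference is 32.65 − 13.64 = 19.0 months.

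**Case 3: unequal follow-up, 0.8 v 0.08 per year.** The true 24-month restricted mean difference is 22.18 − 11.97 = 10.2 in every row. Differences are open minus dilation, in months.

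| Dilation follow-up | Open follow-up | Recurrent only | Censored as recurrences |
|---|---|---|---|
| 36–60 | 36–60 | 10.2 | 26.6 |
| 36–60 | 24–48 | 4.9 | 17.6 |
| 36–60 | 12–36 | −0.3 | 7.7 |
| 36–60 | 6–30 | −2.9 | 2.5 |
| 6–30 | 36–60 | 15.6 | 31.0 |

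**Case 4: no true effect.** Assume 50% recurrence by 36 months in both groups, dilation followed 36 to 60 months and open 6 to 36. The recurrent-only difference is 10.98 − 20.50 = −9.5 months. With censored times counted as recurrences it is 16.79 − 31.14 = −14.4. The restricted mean difference is 0.

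**The case against.** The strongest reply is that the propensity step ends in a regression, and the only regression that the plan names for TTR is Cox. The intended adjusted analysis may therefore be a propensity-adjusted Cox model, with the mean-difference sentence a loose description. That is possible, but the plan does not say it, and the mean-difference sentence is explicit and gives its own reason. The section does describe its approach as an illustration for Aim 2, but Aim 2 is the recurrence aim, so the estimator is not hypothetical.

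Several limits on the size are fair:

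- Sign reversal needs open patients to be followed about 24 months less than dilation patients, or worse. Nothing in the documents predicts that. Those rows are stress tests. At 1.75 v 0.175 per year, even the 6–30 month row gives +2.8, not a negative value.
- Any percentage bias depends on the chosen horizon. In Case 1 the recurrent-only 9.9 happens to match the 24-month restricted mean of 9.8, and with equal follow-up the censored-as-recurrence 25.1 is close to the 48-month value of 25.2. The spread between the two readings does not depend on a horizon.
- Section 2.0 speaks of a 5-year study and Section 16.0 of a three-year follow-up, so the 6-month figure is not the only statement on duration. Neither sets an analysis horizon or a minimum follow-up per patient.
- The instrumental-variable method is of a limited-dependent-variable type and may allow for censoring. That part is a query, not a fault.

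The Kaplan-Meier, logrank and Cox analyses are unaffected.

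**Conclusion.** The concern holds, for the propensity-score analysis only. The plan sets an estimator that treats a censored endpoint as fully observed, and supplies neither a censoring rule nor a horizon. Even with equal follow-up, two literal readings differ by a factor of about 1.7 to 2.7 over the assumed rates. If many open patients never recur, the recurrent-only reading can hide the benefit entirely (0.0 v 19.0 months). With unequal follow-up the error has no fixed direction, and a difference can appear where none exists.

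All sizes rest on assumed rates, exponential times (with a never-recurring fraction in Case 2) and uniform follow-up. The calculations cover open surgery against dilation only. The defect itself rests on none of these assumptions. It should be fixed before analysis, but it does not undermine the primary-endpoint analyses.

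**What to change.** In the selection-bias strategy of Section 12.0, replace the difference-in-means sentence. Suggested wording:

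*The propensity-adjusted treatment effect on TTR will be estimated by a Cox model stratified or weighted by the propensity score, and by the difference in restricted mean recurrence-free time at [horizon] months. Patients without recurrence will be censored at last contact. Follow-up will be reported by treatment group.*

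Either measure would cure the defect. Giving both helps if hazards are not proportional. Fix the horizon in advance at a time that all groups can reach. Thirty-six months is attainable only if enrolment takes 24 months, the study runs 60 and patients are followed to its end; otherwise it must be shorter. State that the later regression on residual covariates uses the same censored outcome and name its variance method.

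In the instrumental-variable paragraph, add one sentence confirming that the second-stage model treats patients without recurrence as censored.

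The cost is wording and slightly more analysis work, with the same data and standard software. The effect would be reported as a hazard ratio or a restricted mean difference instead of a simple mean difference.

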The proposed prospective study (NoAAC PR-02) is designed to fill this void, and leverages and builds upon our previous retrospective multi-institutional investigation, the North American Airway Collaborative RP-01 (NoAAC RP-01). In that study nearly 500 iSGS patients were identified and followed from ten expert tertiary care centers. Specifically, the need for repeat surgery, frequency of disease recurrence, and need for tracheostomy were identified as primary outcome measures.

Collaboration of experienced high volume centers in both the United States and the United Kingdom provided us with the largest and most representative signature of this disease’s epidemiology, natural history, and current management. Inclusion of patients across region and national borders ensured a racially/ethnically representative cohort spanning a range that includes socioeconomic disadvantaged and medically underserved patients. Interestingly, this condition was shown to be quite similar at the separate centers; as it nearly universally affects 40 – 60 year old women (median age 50.3, 95% CI 49.1 – 51.5) who undergo a median 1.75 surgeries per year (95% CI 0.8 – 2.6) (Figure 3). The NoAAC RP-01 study also found variation in the standard of care for iSGS at expert centers. Three basic treatment approaches were used (i.e. endoscopic dilation, endoscopic resection with adjuvant medical therapy, and open anterior neck surgery) despite an absence of randomized controlled trials (RCTs) or other rigorous comparative studies to assess their differential effectiveness at avoiding disease recurrence or tracheostomy.

**Figure 3.** Recurrent nature of interventions in iSGS. Operative procedure number vs. recurrence interval. Each line represents individual patient.

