## 3.0 Inclusion/Exclusion Criteria

### **Inclusion Criteria:**

- >18 years of age.
- The lesion must involve the subglottis.

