### **Exclusion Criteria**

- <18years of age
- Patients without capacity to consent for themselves
- History of significant laryngotracheal traumatic injury.
- History of endotracheal intubation or tracheotomy within 2 years of presentation.
- Major anterior neck surgery.
- History of neck irradiation.
- History of caustic or thermal injuries to the laryngotracheal complex.
- History of a clinically diagnosed vasculitis or collagen vascular disease.
- Positive antinuclear cytoplasmic antibody titers.

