**Protocol.** Once enrolled and consented, patients will receive standard of care treatment at the respective center (Appendix 1) and will be followed longitudinally for symptom changes, need for further treatment, complications, and will have PROs (Appendix 2) administered at *a priori* determined intervals.

**Data collection:** *Data collection for the proposed clinical cohort study will include the following case report forms (CRFs) (Appendix 3), implemented in an electronic data capture (EDC) system (please see further details, below, regarding EDC development and implementation).*

- Baseline. Baseline data will include such things as demographics, medical and surgical history, physical exam findings, and relevant diagnostics
- Procedure. Details of initial surgical procedure will be captured (e.g. site and degree of narrowing within the trachea). This information along with other procedure related information will be abstracted from the operative procedure note and clinical record into the EDC.
- Recurrence. At patient recurrence, information regarding the date of recurrence will be captured as for the initial procedure.
- Patient-reported outcomes (PROs). Validated PRO instruments will be utilized to assess patient quality of life. These relate to voice (VHI-10), dysphagia (EAT-10), breathing (COPD dyspnea), and general quality of life (SF-12). Additionally 4 “Non-traditional” PROs focused on 1) social support, participatory decision-making style, disease anxiety and burden and fear of disease recurrence will also be administered at the initial visit. Patients will be asked to complete “traditional” and “non-traditional PROs at baseline. The “traditional” PROs will be repeated at recurrence, and at routine intervals post-procedure (e.g., at 3, 6, and 12 months). For patients with Internet access and email connectivity, interval PRO completion may be done directly by the patient into the web-based data capture instrument, with automated email reminders to patients at each PRO interval. For patients without Internet/email access, completion of PROs will be via mailed or in person paper forms, or over the phone with a member of the research team; the research staff will then will transfer PRO data from paper to the EDC.

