### *13.1.a: Risks to the subjects*

**Human Subjects Involvement and Characteristics:** Participants are primarily women (with a rare male) newly diagnosed with idiopathic subglottic stenosis identified through clinician providers at one of 30 international sites. There are no racial/ethnic restrictions to enrollment.

**Sources of Materials:** All eligible and willing patients will be asked to complete questionnaires (either written or by telephone, or email) at baseline, and at multiple time points after enrollment. Documented informed consent will be obtained from patients at the time of enrollment in the study, which will include permission to be contacted for future studies by KSP from participating centers.

**Potential Risks:** Minimal risk is anticipated. There are no investigational treatments under study in this project. Study patients will be asked to answer questions on self-administered electronic, mailed, or telephone surveys, and self-reported health data (i.e. peak flow breathing measurements). Additionally, limited information from their routine medical care will be obtained. Patients will be informed that they can refuse to answer any of the questions. They will also be told that refusal to participate in the study will not in any way change or alter the care they will receive. Patients will be told that survey data are to be obtained for research purposes only and that no individual results will be reported. The data will be kept strictly confidential. No data of any sort will be released to anyone outside the study for any reason. Individual patients are never identified in publications.

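### The named confounders in section 12.0 omit the patient's earlier airway procedures and time since diagnosis, although the eligibility criteria admit previously treated patients

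*Combined protocol and SAP*

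**What the plan says.** **Who enters.** The synopsis states: "All clinically confirmed iSGS patients at the participating institutions are eligible for enrolment". The inclusion criteria in section 3.0 add only age and "The lesion must involve the subglottis". Two exclusion criteria touch earlier procedures: "Major anterior neck surgery" and "History of endotracheal intubation or tracheotomy within 2 years of presentation". Neither names earlier endoscopic dilation or endoscopic resection. Section 13.1.a describes participants differently, as "newly diagnosed with idiopathic subglottic stenosis identified through clinician providers".

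**What is adjusted for.** Section 12.0, in its strategy for confounding by selection bias, says: "All known and measurable covariates and confounders will be collected and considered in the propensity score model". The next sentence says that entry into the multivariable model is settled in advance and lists the variables.

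**What is collected.** Section 5.0: "Baseline data will include such things as demographics, medical and surgical history", together with examination findings and diagnostics.

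**What the background shows.** Section 1.0 reports a median of 1.75 surgeries per year in the earlier retrospective cohort. It also captions Figure 3: "Operative procedure number vs. recurrence interval".

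**The concern.** Repeated surgery is the defining feature of this disease as the protocol describes it. How often and how recently a patient has needed a procedure is a natural candidate both to predict the next recurrence and to influence the choice of treatment. Section 12.0 itself warns that outcome differences may depend on characteristics that affected which treatment a patient received.

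If previously treated patients can enter and their history is not in the adjustment set, part of an adjusted difference between dilation, resection and open surgery could reflect how active the disease already was. The propensity and regression models are the plan's main protection for that comparison, so leaving out a measurable disease-history variable weakens them where they are most needed.

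**Working it through.** **Step 1: can previously treated patients enter?**
- Synopsis: all confirmed patients, with no requirement of being untreated.
- Section 3.0: earlier major anterior neck surgery is excluded for everyone, so the question mainly concerns earlier endoscopic procedures, which are not excluded.
- Section 13.1.a: newly diagnosed. This is a description in the human-subjects section, not an eligibility criterion, and a new diagnosis does not by itself mean untreated.

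The operative criteria therefore admit such patients, and one descriptive passage points the other way.

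**Step 2: is the history in the named list?** Counting the list in section 12.0: demographics 6, health 2, endocrine 4, biomarkers 4, anatomy 3, physiology 2, social/behavioural 4. That is 6 + 2 + 4 + 4 + 3 + 2 + 4 = 25 patient variables. With 4 provider variables the total is 29. No item is a count, date or spacing of the patient's own procedures, or disease duration. Procedural volume is listed, but as a provider characteristic. Timing after recurrence appears only among the exploratory subgroup variables.

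**Step 3: which analysis does the list feed?** It feeds the propensity and multivariable comparison. The primary analysis is Kaplan-Meier estimation with a logrank test, both unadjusted, plus a Cox model that gives age as an example of a prognostic factor.

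**Step 4: how large could the effect be?** The plan has no figure to reproduce on this point: it states no share of previously treated patients and no effect of history on recurrence. From the plan come only the group sizes, about 800 for dilation and 100 for each comparison group. All other inputs below are assumptions, and the true treatment hazard ratio is set to 1.

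*Illustration A, history as a count.* Each earlier procedure multiplies the hazard by h (1.1 or 1.2), and the dilation group averages d more procedures (1 or 2). The spurious hazard ratio, comparison group against dilation, is exp(−d × ln h):
- h = 1.1, d = 1: exp(−0.095) = 0.91
- h = 1.2, d = 2: exp(−0.365) = 0.69

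*Illustration B, history as heavy or not.* Heavy history multiplies the hazard by θ, with prevalence pD under dilation and pO in the comparison group. The spurious ratio, dilation against comparison, is approximately [1 + pD(θ − 1)] / [1 + pO(θ − 1)]. For θ = 2 and 60% against 40%, this is 1.6/1.4 = 1.14.

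| θ | 50% vs 40% | 60% vs 40% | 70% vs 30% |
|---|---|---|---|
| 1.5 | 1.04 | 1.08 | 1.17 |
| 2 | 1.07 | 1.14 | 1.31 |
| 3 | 1.11 | 1.22 | 1.50 |

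With equal prevalence the ratio is 1.00. A and B show the same direction of bias with the ratio inverted. If the comparison group had the heavier history, both would flip.

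*Simulation check of B.* Cox models, 800 against 100 patients, baseline rate 0.3 per year, censoring at 2 years, 150 runs per scenario:
- θ = 2, 60% vs 40%: hazard ratio 1.15 without history, rejecting in 12.7% of runs; 1.00 with history, rejecting in 4.0%.
- θ = 1.5, 70% vs 30%: 1.17 and 12.7% without history; 0.99 and 3.3% with it.
- θ = 1.5, 60% vs 40%: 1.105 without history, rejecting in 4.0%, so no visible inflation.

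The Monte Carlo standard error of a 12.7% rate is √(0.127 × 0.873/150) = 0.027, so these rates are approximate.

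**The case against.** **The catch-all wording.** The opening sentence covers every known and measurable confounder, the instrumental-variable paragraph refers to the list as examples, and surgical history is collected at baseline. The plan therefore permits the variable. This stands, and it limits the point: the history is not named in advance, which does not show that it will be left out. But the plan says that entry into the multivariable model is decided beforehand and then lists what enters. Permission is not specification.

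**Other protection.** Scar length, luminal obstruction and pulmonary function may carry part of the history, and the distance instrument is meant for unobserved confounding. Partial capture is plausible, so both illustrations, which assume none, probably overstate what would remain after adjustment. Still, anatomy at one time point does not measure the pace of recurrence, and an instrument with five assumptions does not replace a variable that can be observed.

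**The premise.** Besides section 13.1.a, section 5.0 speaks of the initial procedure, and section 1.0 places the first questionnaires at initial presentation. If the cohort is in fact largely untreated at entry, the problem largely disappears. The eligibility text does not settle this. A reader might infer that the synopsis is right and section 13.1.a should be changed to match; the documents support only reconciling them.

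**Figure 3.** Only the caption is available. It shows that procedure number and recurrence interval were examined together, not that one predicts the other.

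**Conclusion.** The point holds as a gap in the named adjustment set, joined to an unresolved conflict over who enters. Confounding remains only if history differs between treatment groups and predicts recurrence beyond what the 29 listed covariates capture. The documents give neither quantity, so size and direction are unknown. The assumed inputs span spurious hazard ratios from near 1 to about 0.7, or 1.04 to 1.5 inverted, and no bias under balance.

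Four stronger readings are not supported:
- *That the primary logrank comparison is distorted by this list.* That test is unadjusted and the list does not feed it.
- *That false positives reach 87%.* With SE = √[1/(800e) + 1/(100e)] and event fraction e of 0.5 or 0.8 (SE 0.150 or 0.119), the inputs of illustration A do give 9.7% to 87%. But every input except the group sizes is assumed, no capture by listed covariates is allowed for, and 87% is the extreme corner.
- *That imbalance is built in by the exclusion of neck surgery.* That exclusion applies to all groups; imbalance would have to come from treatment selection.
- *That the start of the time-to-recurrence clock is also at fault.* That is a separate question, and nothing here shows a defect in it.

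**What to change.** 1. Reconcile the synopsis, section 3.0 and section 13.1.a on whether previously treated patients enter.
2. Add the number of earlier airway procedures (with none as a valid value) and time since diagnosis to the covariate list in section 12.0, for both the propensity and the outcome model.
3. If procedure dates are recorded, add time since the last procedure, but only as a term nested within previously treated patients (multiplied by an indicator of any earlier procedure). It is undefined for the others and cannot enter as an ordinary covariate.
4. Report a sensitivity analysis in patients with no earlier procedure.

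The cost is SAP wording, plus a check that the baseline form records the count and the dates. The form itself is in an appendix that is not in the reviewed text, so this cannot be taken for granted. Two or three parameters are added to a model that already has 29 covariates and interactions, with about 100 patients in each smaller group. The sensitivity analysis will be less precise to an extent that depends on the unknown share of untreated patients. The change should be made before outcomes are compared between groups. It leaves the unadjusted Kaplan-Meier and logrank analysis as it is.
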